3.1.12 Subject has fasting cholesterol panel and triglyceride done before first treatment

3.1.13 Must be able to swallow ribociclib / placebo capsules

3.2 Exclusion Criteria:

Subjects meeting any of the exclusion criteria at baseline will be excluded from study participation.

3.2.1 Current use of other investigational agents.

3.2.2 Inflammatory breast cancer defined as clinically significant erythema of the breast and/or documented dermal lymphatic invasion (not direct skin invasion by tumor or peau d'orange without erythema).

3.2.3 An excisional biopsy of this breast cancer

3.2.4 Surgical axillary staging procedure prior to study entry.

Note: FNA or core needle biopsy of axillary node is permitted.

3.2.5 Hormone replacement therapy of any type, megestrol acetate, or raloxifene within four weeks prior to first study treatment.

3.2.6 Clinical or radiographic evidence of metastatic disease. Metastatic workup is not required.

Note: isolated ipsilateral supraclavicular node involvement is permitted

3.2.7 Treatment for this cancer including surgery, radiation therapy, chemotherapy, biotherapy, hormonal therapy or investigational agent prior to study entry.

3.2.8 History of invasive breast cancer prior to the current diagnosis.

3.2.9 Patient has a known hypersensitivity to any of the excipients of ribociclib or Letrozole.

3.2.10 Patient has a concurrent malignancy or malignancy within 3 years prior to starting study drug, with the exception of adequately treated, basal or squamous cell carcinoma, non-melanomatous skin cancer or curatively resected cervical cancer.

3.2.11 Patient has impairment of gastrointestinal (GI) function or GI disease that may significantly alter the absorption of the study drugs (e.g., ulcerative diseases, uncontrolled nausea, vomiting, diarrhea, malabsorption syndrome, or small bowel resection).

3.2.12 Patient has a known history of HIV infection (testing is not mandatory).

3.2.13 Patient has any other concurrent severe and/or uncontrolled medical conditions that would, in the investigator's judgment, cause unacceptable safety risks, contraindicate patient participation in the clinical study or compromise compliance with the protocol

(e.g. chronic pancreatitis, chronic active hepatitis, active untreated or uncontrolled fungal, bacterial or viral infections, etc.). Hepatitis testing at screening is not mandatory, but may be done per investigator discretion.

- 3.2.14** Patient has had major surgery within 14 days prior to starting study drug or has not recovered from major side effects (tumor biopsy is not considered a major surgery).
- 3.2.15** Patient with Child-Pugh score B or C
- 3.2.16** Patient has a history of non-compliance to medical regimen or inability to grant consent.
- 3.2.17** Patient is currently receiving or has received systemic corticosteroids ≤ 2 weeks prior to starting study drug, or who have not fully recovered from side effects of such treatment.
- 3.2.18** Patient is currently receiving warfarin or other coumarin-derived anticoagulant for treatment, prophylaxis or otherwise. Therapy with heparin, low molecular weight heparin (LMWH) or fondaparinux is allowed
- 3.2.19** Clinically significant, uncontrolled heart disease and/or recent events including any of the following:
- History of acute coronary syndromes (including myocardial infarction, unstable angina, coronary artery bypass grafting, coronary angioplasty, or stenting) or symptomatic pericarditis within 12 months prior to screening.
 - History of documented congestive heart failure (New York Heart Association functional classification III-IV)
 - Documented cardiomyopathy
 - Patient has a Left Ventricular Ejection Fraction (LVEF) $< 50\%$ as determined by Multiple Gated acquisition (MUGA) scan or echocardiogram (ECHO) at screening
 - History of any cardiac arrhythmias, e.g., ventricular, supraventricular, nodal arrhythmias, or conduction abnormality within 12 months of screening
 - Congenital long QT syndrome or family history of long QT syndrome
 - Bradycardia (heart rate < 50 at rest), by ECG or pulse, at screening
 - Systolic blood pressure (SBP) > 160 mmHg or < 90 mmHg at screening.
- 3.2.20** On screening, inability to determine the QTcF interval on the ECG (i.e.: unreadable or not interpretable) or QTcF > 450 msec (using Fridericia's correction). All as determined by screening ECG.
- 3.2.21** Patient is currently receiving any of the following medications and cannot be discontinued 7 days prior to starting study drug (**APPENDIX B**):
- Known strong inducers or inhibitors of CYP3A4/5, including grapefruit, grapefruit hybrids, pomelos, star fruit, and Seville oranges
 - Those having a narrow therapeutic window and are predominantly metabolized through CYP3A4/5
 - Those having a known risk to prolong the QT interval or induce Torsades de Pointes
 - Herbal preparations/medications as listed in Appendix B

3.3 Staging Criteria:

Subjects will be staged prior to registration according to the clinical staging criteria adapted from the American Joint Committee on Cancer (AJCC) Cancer Staging Data Forms of the AJCC

Cancer Staging Manual, 7th Edition, 2009.

4.0 TREATMENT

4.1 Treatment Dosage and Administration:

Arm A (Control):

Agent	Dose and Route	Day	Schedule
Letrozole	2.5 mg daily by mouth	Days 1-28	Every 4 weeks x 6 cycles
Ribociclib matching placebo (random assignment of placebo)	3 capsules daily by mouth or 2 capsules daily by mouth	Days 1-21 (21 days on, 7 days off) or Days 1-28	

Arm B (Experimental):

Agent	Dose and Route	Day	Schedule
Letrozole	2.5 mg daily by mouth	Days 1-28	Every 4 weeks x 6 cycles
Ribociclib	600 mg daily by mouth (3 capsules of 200 mg)	Days 1-21 (21 days on, 7 days off)	

Arm C (Experimental):

Agent	Dose and Route	Day	Schedule
Letrozole	2.5 mg daily by mouth	Days 1-28	Every 4 weeks x 6 cycles
Ribociclib	400 mg daily by mouth (2 capsules of 200 mg)	Days 1-28	

- Protocol treatment to begin within 14 days of randomization
- Each cycle is 28 days (+/-3 days) or 4 weeks, except cycle 6 (see below).
- Surgery must be performed between days 8-22 of cycle 6.

4.1.1 Ribociclib or Placebo must be taken as follows:

- Subjects should be instructed to take the ribociclib/placebo capsules with a large glass of water (~250mL) at the same time each day.

- Ribociclib can be taken without regard to meals; however, dietary habits around the time of dosing should be as consistent as possible throughout the study.
- Subjects should be instructed to swallow the ribociclib/placebo capsules whole and not to chew, crush or open them.
- If vomiting occurs during the course of treatment, no re-dosing of the subjects is allowed before the next scheduled dose.
- Any doses that are missed (not taken within 6 hours of the intended time) should be skipped and should not be replaced or made up on a subsequent day.
- Subjects must avoid consumption of grapefruit, Seville oranges, star fruit, pomelos, or products containing the juice of each during the entire study and preferably 7 days before the first dose of study medication, due to potential CYP3A4 interaction with the study medications. Orange juice is allowed.

4.1.2 Letrozole should be taken at the same time each day with water.

4.2 Treatment assignment and randomization:

- 4.3.4** MRI of the breast will be performed after completion of 2 cycles of treatment (Day 1 of cycle 3 (+/- 7 days) for response assessment. If there is evidence of progression on MRI, subject will be taken off the study and treatment will be provided at the discretion of the treating physician.
- 4.3.5** If there is physical evidence for clinical progression with bi-dimensional measuring tape, ruler or caliper tumor measurements of the primary tumor an MRI should be done to confirm/rule out progressive disease. If there is physical evidence for clinical progression with clinical assessment of the lymph node mass, an ultrasound of the axilla should be done to confirm/rule out progressive disease.
- 4.3.6** If progression is confirmed by MRI of the breast or ultrasound of axilla, subject will be taken off the study and treatment will be provided at the discretion of the treating physician, such as surgery as soon as possible or to begin other anti-neoplastic approaches such as chemotherapy.

NOTE: Other anti-neoplastic approaches such as chemotherapy or radiation must not be administered while the patient is taking study drug.

- 4.3.7** Study drug should be continued until the day before surgery. If immediate surgery is the decision, due to disease progression, collect the core biopsies (two frozen and two formalin fixed) and the correlative blood samples at the time of surgery. See section 9.
- 4.3.8** If the subject is to discontinue her assigned neo-adjuvant therapy and go on to receive non-protocol treatment, correlative blood specimens and core biopsies (two frozen and two formalin fixed) should be obtained before discontinuing assigned neoadjuvant treatment.
- 4.3.9** If disease progression is not confirmed by MRI of breast or US of axilla, study drug may be continued at the investigator's discretion.
- 4.3.10** Clinical progression outside the primary site (i.e., the development of a new breast mass or the development of clinical suspicion for advanced disease) should lead to further imaging evaluation and if confirmed, study drug will be discontinued after correlative samples of the primary tumor have been obtained. Subsequent management is at the investigator's discretion.

4.4 Dose modifications and management of toxicity for Letrozole:

There will be no letrozole dose reductions. If unanticipated grade 3 or 4 toxicity is encountered, which is considered at least possibly related to letrozole, the patient will be discontinued from letrozole therapy. Missed doses of letrozole are not made up.

4.5 Dose modifications and management of toxicity for Ribociclib/Placebo:

For severe adverse reactions the following dose reduction guidelines will be used:

ARM B (Intermittent dosing arm)	Ribociclib/Placebo	
	Dose	Number of capsules
Starting dose	600 mg	3 x 200 mg capsules
First dose reduction	400 mg	2 x 200 mg capsules
Second dose reduction	200 mg	1 x 200 mg capsule
Discontinue	NA	NA

ARM C (Continuous dosing arm)	Ribociclib/Placebo	
	Dose	Number of capsules
Starting dose	400 mg	2 x 200 mg capsules
First dose reduction	200 mg	1 x 200 mg capsule
Discontinue	NA	NA

If a patient discontinues ribociclib/placebo, she will continue on study taking letrozole alone.

If a patient requires a temporary hold of study drug on Day 1 of a cycle, Day 1 will be delayed until patient restarts study drug. There is no need to repeat all procedures listed for Day 1 in Section 5.0.

4.5.1 Ribociclib/Placebo dose adjustment and management recommendation for related hematological adverse reactions:

Toxicity/Grade	Dose Adjustment and Management Recommendations
Thrombocytopenia	
Grade 1 ($\geq 75,000$ /uL)	No dose adjustment required.
Grade 2 (50,000/uL - < 75,000/uL)	Dose interruption until recovery to $\geq 75,000$ /uL. Re-initiate ribociclib/placebo at the same dose.
Grade 3 (25,000/uL - < 50,000/uL)	Dose interruption until recovery to grade $\geq 75,000$ /uL. Re-initiate ribociclib/placebo at the same dose level. If toxicity recurs at grade 3: temporary dose interruption until recovery to $\geq 75,000$ /uL and reduce ribociclib/placebo to the next lower dose level.
Grade 4 (< 25,000/uL)	Dose interruption until recovery to $\geq 75,000$ /uL. Re-initiate ribociclib/placebo at the next lower dose level. If toxicity recurs at grade 4: discontinue ribociclib.
Absolute neutrophil count (ANC)	
Grade 1 ($\geq 1,500$ /uL)	No dose adjustment required.
Grade 2 (1,000 - < 1,500/uL)	No dose adjustment required.
Grade 3 (500 - < 1,000/uL)	Dose interruption until recovery to > 1,000/uL. Re-initiate ribociclib/placebo at the same dose level. If toxicity recurs at grade 3: temporary dose interruption until recovery to > 1,000/uL and reduce ribociclib/placebo dose to the next lower dose level.
Grade 4 (< 500/uL)	Dose interruption until recovery to > 1,000/uL. Re-initiate ribociclib/placebo at the next lower dose level. If toxicity recurs at grade 4: temporary dose interruption until recovery to > 1,000/uL and reduce ribociclib/placebo at the

	next lower dose level.
Febrile neutropenia	
Grade 3 ANC < 1,000/uL with a single temperature > 38.3°C (101°F) or a sustained temperature of ≥ 38°C (100.4°F) for more than one hour	Dose interruption until ANC ≥ 1,000/uL and no fever. Restart at the next lower dose level. If febrile neutropenia recurs: discontinue ribociclib/placebo.
Grade 4 Life-threatening consequences; urgent intervention indicated	Discontinue ribociclib/placebo.
Anemia (Hemoglobin)	
Grade 1 (≥ 10 g/dL)	No dose adjustment required.
Grade 2 (8 – 10 g/dL)	No dose adjustment required.
Grade 3 (< 8 g/dL)	Dose interruption until recovery to ≥ 8 g/dL. Re-initiate ribociclib/placebo at the same dose.
Grade 4 Life-threatening consequences; urgent intervention indicated	Discontinue ribociclib/placebo.

4.5.2 Recommendations for Ribociclib/Placebo dose modification in case of related hepatic toxicities

HEPATOTOXICITY (BILIRUBIN, SGPT/ALT, SGOT/AST)	
TOTAL BILIRUBIN without ALT/AST increase above baseline value	
Grade 1 > IULN – 1.5 x IULN (confirmed 48 to 72hrs later)	Maintain dose level with LFTs monitored bi-weekly
Grade 2 > 1.5 – 3.0 x IULN	Dose interruption of ribociclib/placebo If resolved to ≤ grade 1 in ≤ 21 days, maintain dose level If resolved to ≤ grade 1 in > 21 days or toxicity recurs, reduce 1 dose level If toxicity recurs after two dose reductions, discontinue ribociclib/placebo
Grade 3 > 3.0 – 10.0 x IULN	Dose interruption of ribociclib/placebo If resolved to ≤ grade 1 in ≤ 21 days, reduce 1 dose level If resolved to ≤ grade 1 in > 21 days or toxicity recurs, discontinue ribociclib/placebo
Grade 4 > 10.0 x IULN	Discontinue ribociclib/placebo

Confounding factors and/or alternative causes for increase of total bilirubin should be excluded before dose interruption/reduction. They include but are not limited to: evidence of obstruction, such as elevated ALP and GGT typical of gall bladder or bile duct disease, hyperbilirubinemia due to the indirect component only (i.e. direct bilirubin component $\leq 1 \times \text{IULN}$) due to hemolysis or Gilbert Syndrome, pharmacologic treatment, viral hepatitis, alcoholic or autoimmune hepatitis, other hepatotoxic drugs. Hepatitis testing is not mandatory; to be done per investigator discretion.

For patients with Gilbert Syndrome, these dose modifications apply to changes in direct bilirubin only. Bilirubin will be fractionated if elevated.

HEPATOTOXICITY (BILIRUBIN, SGPT/ALT, SGOT/AST)	
AST or ALT	
AST or ALT without bilirubin elevation $> 2 \times \text{IULN}$	
Same grade as baseline or increase from baseline grade 0 to grade 1 (confirmed 48 to 72 hrs later)	No dose adjustment required with LFTs monitored per protocol if same grade as baseline or bi-weekly, in case of increase from baseline grade 0 to 1.
Increase from baseline grade 0 or 1 to grade 2 $> 3.0 - 5.0 \times \text{IULN}$ or from baseline grade 2 to grade 3 $> 5.0 - 20.0 \times \text{IULN}$	Dose interruption of ribociclib/placebo. If resolved to \leq baseline value in ≤ 21 days, then maintain dose level If resolved to \leq baseline value in > 21 days or toxicity recurs, then reduce 1 dose level If toxicity recurs after two dose reductions or recovery to \leq baseline value is > 28 days, discontinue ribociclib/placebo
Increase from baseline grade 0 or 1 to grade 3 $> 5.0 - 20.0 \times \text{IULN}$	Dose interruption of ribociclib/placebo until resolved to \leq baseline value, then lower 1 dose level of ribociclib/placebo If recovery to \leq baseline value is > 28 days, discontinue ribociclib/placebo If toxicity recurs, discontinue ribociclib/placebo
Grade 4 $> 20.0 \times \text{IULN}$	Discontinue ribociclib/placebo
AST or ALT and concurrent Bilirubin	
AST or ALT \geq grade 2 $> 3 \times \text{IULN}$ in patients with normal values at baseline and total bilirubin $> 2 \times \text{IULN}$ Or AST or ALT \geq grade 3 $> 5 \times \text{IULN}$ in patients with grade 1 or 2 at baseline, and total bilirubin $> 2 \times \text{IULN}$	Discontinue ribociclib/placebo
Confounding factors and/or alternative causes for increased transaminases should be excluded before dose interruption/reduction. They include but are not limited to: concomitant medications, herbal preparations or dietary supplements, infection, hepato-biliary disorder or obstruction, new liver metastasis, and alcohol intake.	

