4.5.3 Additional follow-up for related hepatic toxicities

Hepatic toxicity monitoring includes the following LFTs: albumin, ALT, AST, total bilirubin (fractionated if total bilirubin $> 2 \times \text{IULN}$), alkaline phosphatase (fractionated if alkaline phosphatase is grade 2 or higher) and GGT. For patients with Gilbert Syndrome: total and direct bilirubin must be monitored, intensified monitoring applies to changes in direct bilirubin only.

Close observation is recommended in case of AST, ALT, and/or bilirubin increase requiring dose interruption, which involves:

- Repeating liver enzyme and serum bilirubin tests two or three times weekly. Frequency of re-testing can decrease to once a week or less if abnormalities stabilize or return to normal values.
- Obtaining a more detailed history of current symptoms.
- Obtaining a more detailed history of prior and/or concurrent diseases.
- Obtaining a history of concomitant drug use (including non-prescription medications, herbal and dietary supplements), alcohol use, recreational drug use, and special diets.
- Ruling out acute viral hepatitis types A, B, C, D, and E; hepatotropic virus infections (CMV, EBV or HSV); autoimmune or alcoholic hepatitis; NASH; hypoxic/ischemic hepatopathy; and biliary tract disease. Hepatitis testing is not mandatory; to be done per investigator discretion.
- Obtaining a history of exposure to environmental chemical agents.
- Obtaining additional tests to evaluate liver function, as appropriate (e.g., INR, direct bilirubin).
- Considering gastroenterology or hepatology consultations.
- Assessing cardiovascular dysfunction or impaired liver oxygenation, including hypotension or right heart failure as possible etiologies for liver dysfunction.

4.5.4 Ribociclib/placebo dose adjustment and management recommendation for related non-hematological adverse reactions

Grade	Dose Adjustment and Management Recommendations
1	No dose adjustment required. Initiate appropriate medical therapy and monitor.
2	Dose interruption until recovery to grade ≤ 1 . Initiate appropriate medical therapy and monitor. Re-initiate ribociclib/placebo at the same dose. 
 • If the same toxicity recurs at grade 2, interrupt ribociclib/placebo until recovery to grade ≤ 1. Re-initiate ribociclib/placebo at the next lower dose level.

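### The hepatic dose table in 4.5.2 gives a weaker action, or no row at all, for some combined rises in bilirubin and ALT/AST

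*Combined protocol and SAP*

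**What the plan says.** Section 4.5.2 has three blocks, each with its own entry condition.

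- Bilirubin block: "TOTAL BILIRUBIN without ALT/AST increase above baseline value". Its grade 2 row (above 1.5 to 3.0 x IULN) requires interruption. Grade 3 requires interruption with a lower restart dose or a stop, and grade 4 requires discontinuation.
- ALT/AST block: "AST or ALT without bilirubin elevation" above 2 x IULN. If the enzyme grade is unchanged or moves from 0 to 1, the action is "No dose adjustment required with LFTs monitored per protocol if same grade as baseline or bi-weekly" for the 0-to-1 rise. That row also carries a note about confirmation at 48 to 72 hours. A rise from grade 0 or 1 to grade 2 requires interruption until return to baseline, and a stop applies: "If toxicity recurs after two dose reductions or recovery to" baseline takes more than 28 days.
- Combined block: discontinue if ALT/AST exceeds 3 x with bilirubin above 2 x from a normal baseline, or if ALT/AST exceeds 5 x "in patients with grade 1 or 2 at baseline, and total bilirubin" above 2 x.

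Section 4.5.3 adds intensified follow-up: "Close observation is recommended in case of AST, ALT, and/or bilirubin increase requiring dose interruption". It includes "Repeating liver enzyme and serum bilirubin tests two or three times weekly", with a step-down once results stabilise.

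Section 4.5.4 is a general table for related non-hematological reactions. A first grade 2 event means interruption to grade 1 or below, then "Re-initiate ribociclib/placebo at the same dose". Section 4.5.2 makes no reference to it.

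**The concern.** A dose table should not become more lenient as the liver panel worsens. Here the bilirubin rows switch off as soon as ALT/AST rises above its baseline value, and the ALT/AST rows switch off once bilirubin passes 2 x. The combined block does not pick up everything released by those two conditions. Sites holding the same results could therefore interrupt or continue ribociclib/placebo, depending on whether they stay within 4.5.2 or turn to 4.5.4.

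Monitoring partly follows that choice, because the close observation in 4.5.3 is tied to a rise that requires interruption. What is at stake is consistent handling of possible liver injury. The comparison of PEPI score 0 rates in 16.2 does not depend on this table.

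**Working it through.** The plan states no figure to reproduce. The check is whether each combination of results meets the printed conditions of some row.

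**Inputs.** Scope conditions and grade limits come from 4.5.2. Section 3.1.11 admits ALT/AST below 2.5 x ULN, so a grade 1 baseline is eligible. One assumption is needed: ALT/AST grade 1 means above 1 to 3 x IULN, because the table prints limits only from grade 2 upward (above 3-5, above 5-20, above 20). A rise above baseline is taken as a rise in value. This fits the table, which says grade where it means grade and uses the baseline value as a numeric recovery target. No minimum size of rise is given.

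**Row matching** (multiples of IULN):

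| Baseline ALT | Current ALT | Bilirubin | Matching row(s) in 4.5.2 |
|---|---|---|---|
| 1.5 | 1.5 | 1.8 | Bilirubin grade 2: interrupt; also ALT/AST same grade: no change |
| 1.5 | 2.8 | 1.8 | ALT/AST same grade only: no change, tests on the protocol schedule |
| 0.8 | 2.0 | 1.8 | ALT/AST grade 0 to 1 only: no change, bi-weekly tests |
| 1.5 | 2.8 | 2.5 or 12 | None |
| 1.5 | 4.5 | 1.8 | ALT/AST grade 2: interrupt |
| 1.5 | 4.5 | 2.5 | None |
| 0.8 | 4.5 | 2.5 | Combined: discontinue |
| 1.5 | 5.5 | 2.5 | Combined: discontinue |

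Three patterns emerge.

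1. Bilirubin above 1.5 to 2 x with an enzyme rise that stays grade 0-1. Adding the rise removes the interruption (row 1 against row 2).
2. Bilirubin above 2 x with an enzyme rise that stays grade 0-1. No row applies, even at 12 x.
3. Grade 1 baseline, ALT/AST above 3 to 5 x, bilirubin above 2 x. No row applies, although the same ALT with bilirubin at 1.8 x requires interruption, and the same pair from a normal baseline requires discontinuation.

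Row 1 also shows that two rows can match with different actions, and 4.5.2 has no rule for which prevails.

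**What 4.5.4 would do.** In pattern 1, bilirubin above 1.5 x is grade 2, so 4.5.4 interrupts while the only matching hepatic row does not. In pattern 2 it holds drug, and at bilirubin above 10 x it discontinues. In pattern 3 it also holds drug, but asks only for recovery to grade 1 (ALT/AST at or below 3 x, bilirubin at or below 1.5 x). The return-to-baseline target and the 28-day stop are absent. At bilirubin above 3 to 10 x, 4.5.4 is firm on dose: restart one level lower, and stop if grade 3 recurs.

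**Monitoring in pattern 1.** On the 4.5.2 reading no interruption is required, so 4.5.3 is not triggered. A patient at her baseline grade has scheduled chemistry on day 1 of each 28-day cycle (5.0, 6.4). The end-of-treatment draw is CBC only, so from day 1 of cycle 6 to surgery on days 8-22 (8 - 1 = 7 to 22 - 1 = 21 days) no chemistry is scheduled. The 48-72 hour confirmation may supply one repeat test: the note can be read as attaching to the whole row or only to a 0-to-1 rise.

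**The case against.** The strongest reply is that 4.5.4 already covers these patients and would hold drug at grade 2 or above. That largely stands. A reader might infer that asymptomatic laboratory rises fall outside 4.5.4, because 7.1.1 limits when a laboratory value counts as an adverse event. The documents do not support pressing this. The same section's general definition includes abnormal laboratory findings, 7.2.6 accepts those the investigator judges relevant, and 4.5.1 applies the same term, adverse reactions, to blood counts alone. The narrow reading would empty 4.5.1 as well. What remains is that 4.5.2 does not direct sites to 4.5.4, and in pattern 1 the two give opposite actions.

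A second reply is that the no-adjustment row speaks only to enzyme grade and was never meant to cancel a bilirubin hold. That is probably the intent, but the bilirubin block's own entry condition produces the cancellation.

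A reader might also set one test per 28 days against 8-12 under 4.5.3 (two or three weekly x 4 weeks). That contrast is too strong. The confirmation note may add a test, a 0-to-1 rise gets bi-weekly tests, and 4.5.3 permits stepping down.

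Finally, 4.5 offers guidelines, 6.8.5 and 6.8.6 allow removal for safety, and 16.2 records accrual as almost complete by the time the first 60 patients had PEPI data. These limit harm and the number who would benefit. They do not supply a consistent rule.

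**Conclusion.** The inconsistency is real but narrow. As printed, 4.5.2 gives a weaker action for a worse panel in pattern 1 and no row in patterns 2 and 3. Section 4.5.4 reasonably fills much of the gap, but it conflicts with the hepatic row in pattern 1 and lacks the recovery target and 28-day stop in pattern 3. The monitoring gap is modest, and clearest for patients who stay at their baseline enzyme grade.

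It is probably rare: outside Gilbert's Syndrome, entry requires bilirubin at or below IULN. A reader might look for a frequency in the grade 3 ALT increase in 1 of 18 continuous-dosing patients (1.6). That figure pools 600, 400 and 300 mg and is not a rate of combined rises. Nor does it help to note that ALT or AST would often exceed baseline by chance, since the relevant event also needs bilirubin above 1.5 x. The documents support no frequency estimate.

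The conclusion rests on reading the baseline comparison as a comparison of values and on the grade 1 limits assumed above. It has no bearing on the primary analysis.

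**What to change.** 1. Replace the bilirubin block's entry condition so that its rows apply whenever the combined-block criteria are not met, and state that the stricter action prevails when two rows match. This resolves patterns 1 and 2: 1.5 / 2.8 / 1.8 and 1.5 / 2.8 / 2.5 become interruptions, and 1.5 / 2.8 / 12 a discontinuation.
2. For a grade 1 baseline with ALT/AST above 3 to 5 x and bilirubin above 2 x, apply the existing ALT/AST grade 2 row (interrupt to baseline, its dose rules, stop if recovery exceeds 28 days) together with the bilirubin row, stricter action prevailing. A new mandatory dose reduction is not needed: the ALT/AST grade 2 row allows the same dose after recovery within 21 days. Leave the 5 x discontinuation threshold as it is.
3. State that 4.5.2, not 4.5.4, governs liver tests.

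The cost is an amendment to one table, a few more interruptions or discontinuations of ribociclib/placebo, and the repeat tests that interruptions bring under 4.5.3. In Arm C the only reduction step is 400 to 200 mg, so a second reduction means stopping. Letrozole continues under 4.5. The benefit reaches only patients still taking ribociclib/placebo when the amendment takes effect.
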